#### **8.2.1.5 Relevant changes to background medication**

For purposes of this secondary efficacy variable, relevant changes to background medication will be defined as the following:

- The addition of a new DMARD or the change from one DMARD to another
- The addition of an NSAID or the change from one NSAID to another
- Increased dose of chronic oral corticosteroids
- Increased dose in chronic analgesic medications or the addition of a chronic analgesic medication

The variable to be measured is the number of subjects without relevant changes to background medications. Therefore, a subject who does not have any of the above relevant changes made to background medication during the study through Week 52 will be considered to have met this endpoint. Conversely, subjects who have one of the above relevant background medication changes or who do not complete double-blind study treatment to Week 52 will be considered as not having met this endpoint.

#### **8.2.1.6 Ankylosing Spondylitis Quality of Life (ASQoL)**

The ASQoL, a validated disease-specific 18-item questionnaire, has been developed specifically for measuring HRQoL in subjects with AS (Doward et al, 2003). A nonradiographic axSpA (nr-axSpA) specific scoring algorithm is presently being developed, but it is unclear when this algorithm will become available relative to the timing of the AS0006 database lock. Should this alternative scoring approach become available prior to finalization of the clinical study report, analyses of ASQoL data may be repeated using this alternate scoring approach appropriate for nr-axSpA population and methods will be described either in a SAP amendment or within the Documentation of Statistical Methods appendix to the study report.

#### **8.2.1.7 Nocturnal Spinal Pain**

Nocturnal spinal pain will be recorded based on a NRS ranging from 0 to 10, where 0 represents no pain and 10 represents most severe pain.

#### **8.2.2 Primary analysis of the secondary efficacy variables**

The comparison of CZP 200mg Q2W to placebo as described in this section for the ASAS40 response, BASDAI, and BASFI at Week 12 and Week 52, SI joint SPARCC score at Week 12, ASQoL at Week 52 and Nocturnal Spinal Pain at Week 52 will be part of the fixed sequence testing procedure outlined in [Section 8](#).

### **8.2.2.1 Primary analysis of categorical secondary efficacy variables**

The ASAS40 response at Week 12 and Week 52 are responder secondary efficacy variables. For Canada and any other country where applicable or where requested by Regulatory Authorities, the ASAS40 response at Week 12 is the primary efficacy variable; the ASAS40 response at Week 52 and the ASDAS-MI response at Week 52 are secondary efficacy variables. Hence the primary and sensitivity efficacy analysis on ASDAS-MI at Week 52 will be repeated for ASAS40 at Week 12.

As a responder variable, ASAS40 will be analyzed using logistic regression in the same manner as for the primary analysis described in [Section 8.1.2](#). As with the primary efficacy variable, the ASAS40 will be treated as a composite endpoint when it is analyzed. Specifically, subjects will need to 1) achieve the relevant response (ASAS40) and 2) remain in the study and on their randomized double-blind study treatment through the time point being analyzed (Week 12 or Week 52).

Relevant changes to background medication will also be analyzed using the same composite endpoint logistic regression model described for the primary variable described in [Section 8.1.2](#).

The number of subjects with new onset post-Baseline AU or new AU flares through Week 52 is a categorical secondary efficacy endpoint for all regions. Subjects will be classified as having post-Baseline Uveitis: a TEAE of Uveitis, a new diagnosis of Uveitis or a flare of uveitis at any visit post-Baseline which is on or before the Week 52 visit. All subjects without evidence of uveitis events, new diagnosis or flares will be considered not to have post-Baseline Uveitis. As a dichotomous outcome variable, treatment groups will be compared for differences using logistic regression including treatment, region and MRI/CRP classification as explanatory variables. Subjects with no evidence of new AU flares will be considered as having no flare.

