## 8 EFFICACY ANALYSES

All efficacy analyses of the double-blind 52-week treatment period will be performed using the FAS. The PPS and Randomized Set will be used for a sensitivity analysis on the primary endpoint only (using the composite endpoint analysis). The SFE-FAS will be used for analysis of efficacy data at the Week 156/SFE-WD visit.

The statistical analysis of the primary efficacy variable and selected secondary efficacy variables will account for multiplicity by using a fixed sequence testing procedure. The predefined order of hypotheses testing, each at a 2-sided 0.05 significance level for the comparison between CZP 200mg Q2W and placebo, will be performed in the sequence shown below. After the first test, each subsequent test is performed only if the previous test is significant in favor of CZP at the 2-sided 0.05 level. Note that the first test relates to the primary efficacy variable while the others provide the sequential testing for selected secondary efficacy variables:

Primary:

1. ASDAS-MI response at Week 52 (Composite endpoint analysis)

Secondary:

2. ASAS40 response at Week 12 (Composite endpoint analysis)
3. Change from Baseline in BASDAI at Week 12 (Reference based multiple imputation analysis)
4. Change from Baseline in BASFI at Week 12 (Reference based multiple imputation analysis)
5. ASAS40 response at Week 52 (Composite endpoint analysis)
6. Change from Baseline in BASDAI at Week 52 (Reference based multiple imputation analysis)
7. Change from Baseline in BASFI at Week 52 (Reference based multiple imputation analysis)
8. Change from Baseline in SI joint SPARCC score at Week 12 (Reference based multiple imputation analysis)
9. Change from Baseline in ASQoL at Week 52 (Reference based multiple imputation analysis)

10. Change from Baseline in nocturnal spinal pain (NRS) at Week 52 (Reference based multiple imputation analysis)

11. Number of subjects with AU or new AU flares through Week 52

Hierarchical testing of efficacy variables for Canada (and any other country where applicable or where requested by Regulatory Authorities):

Primary:

1. ASAS40 response at Week 12 (Composite endpoint analysis)

Secondary:

2. ASDAS-MI response at Week 52 (Composite endpoint analysis)

3. Change from Baseline in BASDAI at Week 12 (Reference based multiple imputation analysis)

4. Change from Baseline in BASFI at Week 12 (Reference based multiple imputation analysis)

5. ASAS40 response at Week 52 (Composite endpoint analysis)

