### 8.1.2 Primary analysis of the primary efficacy variable

The primary analysis for of the primary efficacy variable will be based on logistic regression. The odds ratio of the ASDAS-MI responder rates at Week 52 will be estimated and tested between treatment groups using a logistic regression model with factors of treatment group, region, and MRI/CRP classification (MRI+/CRP+; MRI+/CRP-; MRI-/CRP+). The MRI/CRP classification used in all statistical analysis will be recalculated using source data as described in [Section 4.8](#) and the IXRS MRI/CRP categorization will not be used. If the logistic regression model is unable to converge, then the MRI/CRP classification variable may be dropped from the model to facilitate convergence. The study design is likely to result in some sites with a small number of enrolled subjects. The use of region as a factor in the model is intended to combine study centers in similar geographic regions. The geographic regions to be used will be as defined in the IXRS randomization system. In the unlikely event that a subject moves sites during the study which leads to a change in region, the region originally used at randomization will be used in the analysis.

Given the composite endpoint definition described in [Section 8.1](#), there will be no missing data for the primary endpoint, as subjects that discontinue double-blind study treatment prior to Week 52 or who do not have an ASDAS-MI response at Week 52 are considered non-responders to the double-blind study treatment.

Tables will present the responder rates for placebo and CZP 200mg, the respective effect estimates (adjusted odds ratio with reference to placebo), p-values, and 95% confidence intervals (CIs). The odds ratios and 95% CIs will also be presented graphically.

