## 8.2 Statistical analysis of secondary efficacy variables

The secondary efficacy variables are designated as variables 2 through 11 in the hierarchical testing procedure outlined in [Section 8](#), in addition to counts of relevant changes to background medication. The statistical methodology to be used for the analysis of these variables is described below.

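### The anterior uveitis (AU) test, last in both fixed sequences, names no test statistic and no sparse-event method; under Wald inference it cannot succeed if one arm has no events

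*SAP*

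**What the plan says.** SAP Section 8 lists as the final test, in the main and the Canada sequence alike, "11. Number of subjects with AU or new AU flares through Week 52". Every test in the main sequence is made "each at a 2-sided 0.05 significance level for the comparison between CZP 200mg Q2W and placebo". Section 8.2 confirms the position: "The secondary efficacy variables are designated as variables 2 through 11 in the hierarchical testing procedure".

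For AU, Section 8.2.2.1 says that "treatment groups will be compared for differences using logistic regression including treatment, region and MRI/CRP classification as explanatory variables". It adds: "Subjects with no evidence of new AU flares will be considered as having no flare". Every subject is therefore classified, and an arm can have no events at all.

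The only rule for a model that fails is in Section 8.1.2, for the primary variable: "If the logistic regression model is unable to converge, then the MRI/CRP classification variable may be dropped from the model to facilitate convergence". Section 8.3 repeats it for the other categorical variables. Section 8.2.2.1 ties ASAS40 and background medication to Section 8.1.2, but not AU.

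Section 8.2.2 names the variables in the fixed sequence and ends with "ASQoL at Week 52 and Nocturnal Spinal Pain at Week 52 will be part of the fixed sequence testing procedure outlined in" Section 8. AU is not named there.

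**The concern.** A 52-week count of subjects with uveitis may be small in a trial of this size. Ordinary logistic regression behaves badly in that setting. With an empty arm the treatment log odds ratio has no finite maximum-likelihood estimate, its standard error explodes, and a Wald test reports no evidence. The test would then fail on the most extreme split of the data while passing a milder one.

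What is at stake is a claim under type I error control. If the separation appears only after unblinding, the plan offers no agreed way to obtain a valid p-value, and a method chosen at that point would carry little weight.

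**Working it through.** **Inputs.** From the SAP: 150 per arm, 1:1 allocation, 2-sided 0.05 (Sections 2.4 and 8); factors treatment, region (3 levels) and MRI/CRP (3 levels), so four covariate parameters plus treatment. Assumed, because the SAP gives none: AU rates, and stratum sizes per arm of 30/100/20 for region and 50/50/50 for MRI/CRP.

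**1. The SAP's own power figure.** The only one is 95% for ASDAS-MI, 40% vs 20%. Power = Φ[(0.20 − 1.96·√(2·0.30·0.70/150)) / √((0.40·0.60 + 0.20·0.80)/150)] = Φ(1.86) = 96.9%; exact Fisher power is 96.0%. This agrees with the stated 95%. No figure is given for AU.

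**2. What the Wald test does at a zero cell.** With *a* CZP and *b* placebo events:
- log OR = ln[a(150 − b) / (b(150 − a))], SE = √(1/a + 1/(150 − a) + 1/b + 1/(150 − b)).
- 1 vs 8: log OR = ln[142/(8·149)] = −2.128, SE = 1.067, z = −1.99, p = 0.046.
- 0 vs 8: as *a* goes to 0, the log OR diverges but the SE grows faster, so z goes to 0 and p to 1. From the same data the likelihood-ratio statistic is 11.31 on 1 df, p = 0.0008, and Fisher gives 0.007.

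**3. The same check in the planned adjusted model.** Zero CZP events, placebo events placed at random (60 placements; 10 for Firth), median p:

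| Placebo events | Wald | Wald, MRI/CRP dropped | Likelihood ratio | Firth penalized LR | Fisher |
|---|---|---|---|---|---|
| 3 | 0.997 | 0.997 | 0.040 | 0.11 | 0.25 |
| 5 | 0.996 | 0.996 | 0.008 | 0.026 | 0.060 |
| 6 | 0.995 | 0.996 | 0.004 | 0.013 | 0.030 |
| 8 | 0.993 | 0.993 | 0.0008 | 0.003 | 0.007 |
| 10 | 0.993 | 0.993 | 0.0002 | 0.0007 | 0.002 |

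The fitted treatment coefficient is about −18 with SE about 2,000 to 4,900. Dropping MRI/CRP changes nothing, because treatment is the separating variable.

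**4. How often it could happen.** P(no CZP events) = (1 − p)^150, which is 47%, 22% and 5% at true rates of 0.5%, 1% and 2%.

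**5. Power, unadjusted, by exact enumeration.** Wald is counted as not significant at a zero cell.

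| Placebo vs CZP | Wald | Fisher |
|---|---|---|
| 5% vs 0.5% | 22% | 56% |
| 5% vs 1% | 26% | 40% |
| 8% vs 1% | 63% | 81% |
| 8% vs 2% | 60% | 58% |
| 10% vs 3% | 67% | 63% |
| 12% vs 4% | 72% | 67% |

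The loss comes entirely from the zero cell. At 5% vs 1%, Fisher's 40% is about 17% from trials with no CZP events plus 23% from the rest; Wald's 26% comes only from the rest.

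**The case against.** The strongest reply is that Section 8.2.2.1 says neither maximum likelihood nor Wald. A likelihood-ratio test of the same model gives 0.004 at 0 vs 6, so a reader who infers that the planned test must return a p-value near 1 goes beyond the text. That stands: the Wald reading is an inference. It rests on usual practice and on Section 8.1.3.2, where the same logistic model (with Baseline added) is pooled from estimates and standard errors through PROC MIANALYZE, which is Wald-type. The reply also shows the gap: the verdict on a controlled test turns on a choice the plan does not make.

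Other stronger readings are not supported:
- **AU events are certain to be few.** The SAP gives no rates. Above about 2% on CZP the Wald test matches or beats Fisher in most of the cases examined.
- **The chance of no CZP events is the chance of losing the claim.** It overstates it, since 0 vs 5 is not significant by Fisher either (0.060). At 5% on placebo, the chance of an empty CZP arm with a significant Fisher result is 36%, 17% and 3.7% for CZP rates of 0.5%, 1% and 2%.
- **Other conclusions are affected.** No test follows AU in either sequence, and it is reached only if the ten before it succeed.
- **Section 8.2.2 takes AU out of the sequence.** Its list does not claim to be complete, and Sections 8 and 8.2 include AU. The omission is editorial.

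It is also fair to say that the power table compares Wald with unadjusted Fisher. Firth was examined only through p-values in zero-cell data; its power and type I error were not simulated.

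**Conclusion.** The point holds as a weakness in how test 11 is specified. Under Wald inference an empty arm makes success impossible: 0 vs 8 fails while 1 vs 8 passes at 0.046. The convergence rule elsewhere in the SAP is not written for AU and would not help if it were. Under assumed rates the cost runs from 34 percentage points of power (5% vs 0.5%: 56 − 22) through 14 (5% vs 1%: 40 − 26) to none (8% vs 2%). These figures rest on the Wald reading, on assumed event rates and on unadjusted comparisons. The consequence is limited to the AU claim, so this should be corrected but does not threaten the primary result.

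**What to change.** In Section 8.2.2.1, for both sequences, name the AU test as Firth-penalized logistic regression with treatment, region and MRI/CRP, reporting a profile penalized-likelihood p-value and CI. This keeps the planned factors and the odds ratio. An unadjusted exact test is not preferred: it gives up about 4 to 5 points when events are not sparse (10% vs 3% and 12% vs 4%). Naming the ordinary likelihood-ratio test is not enough either: at 0 vs 3 it gives 0.040 where Fisher gives 0.25.

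The timing limits what the change can do. Sections 2.2.1.3 and 8.1.1 show that this version follows the Week 52 lock outputs, and Section 4.3 releases the treatment codes to the reporting team at that lock. The SAP or study report should therefore state which statistic decided test 11. If the Firth analysis was not specified before unblinding, it should be labelled supportive.

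AU should also be added to the list in Section 8.2.2, as an editorial correction. The cost is a sentence or two of text and one option in the logistic procedure; a short simulation of Firth's rejection rate at low event counts would be worth adding.

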### **8.2.2.2 Primary analysis of continuous secondary efficacy variables**

The continuous BASDAI, BASFI, ASQoL and Nocturnal Spinal Pain score at each visit will be calculated using the methods described in [Sections 8.2.1.2, 8.2.1.3, 8.2.1.6 and 8.2.1.7](#). Missing data (including data excluded due to subjects discontinuing double-blind study treatment) at each visit will be handled via reference based multiple imputation as described below:

The reference-based multiple imputation assumes that the statistical behavior of the CZP and placebo-treated subjects after discontinuing study medication becomes that of the placebo-treated subjects. Data collected after discontinuation of the double-blind study treatment for both the CZP and placebo groups will be considered missing. Multiple imputations are used to replace missing outcomes for drug- and placebo-treated subjects who discontinued using multiple draws from the posterior predictive distribution estimated from the placebo arm. For binary efficacy variables (ASAS40 at Weeks 12 and 52), imputation will be done on the raw components before assessing the imputed results for ASAS response. For continuous efficacy variables (change from Baseline in BASDAI and BASFI at Weeks 12 and 52, change from Baseline in the SI joint SPARCC score at Week 12, change from baseline in ASQoL and Nocturnal Spinal Pain at Week 52), imputation will be done on the raw scores prior to calculating the change from Baseline.

1. For subjects with a non-monotone (intermittent) missing pattern, MCMC will be used to impute their missing intermittent scores including treatment, region and MRI/CRP

classification as explanatory variables. This will be done 100 times in order to provide a dataset with monotone missing limiting imputation to in range results.

After this step there will be 100 datasets containing all subjects however the only missing data will be a monotone missing data pattern. A variable called “\_imputation\_” will identify each of the 100 imputed datasets output.

2. The remaining missing data for all subjects with a monotone missing data pattern will be imputed using regression using the placebo-treated subjects arm only to impute missing data for both placebo and CZP treatments. The model will contain region, MRI/CRP classification and measurement from previous visit(s) as explanatory variables. This model will be run once for each of the imputed datasets limiting imputation to in range results.
3. For each completed data set, the outcome (response or change from Baseline) will be calculated using the complete datasets (with no missing data).
4. For ASAS40, complete parts 5 and 6 from [Section 8.1.3.2](#) in order to provide odds ratios, 95% CIs and the p-value from the proc mianalyze. For BASDAI, BASFI, SI joint SPARCC, ASQoL and Nocturnal Spinal Pain, complete parts 4 and 5 from [Section 8.2.2.2](#) in order to provide treatment differences, 95% CIs and the p-value from the proc mianalyze.

Additionally, change from Baseline in SI joint SPARCC score at Week 12 is a continuous secondary efficacy variable. The same referenced based multiple imputation procedure specified in this section will be used to account for missing SPARCC data. However, it should be noted that, unlike BASDAI and BASFI, SPARCC score will not be measured at any time points between Baseline and Week 12, meaning that those are the only 2 time points that can be considered in the evaluation of SPARCC score at Week 12. Comparisons between treatment groups will be made using an analysis of covariance (ANCOVA) model on the imputed data set. The model will include Baseline score, treatment group, region, and MRI/CRP classification.

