## **2.4 Determination of sample size**

Subjects will be randomized in a 1:1 ratio to the CZP 200mg Q2W and placebo treatment groups. The expected response rates for ASDAS-MI at Week 52 are 40% and 20% for CZP and placebo, respectively. A total sample size of 300 (150 subjects per treatment group) provides 95% power to detect a statistically significant difference in the ASDAS-MI response rate at Week 52 between CZP and placebo based on a 2-sided significance level of 0.05.

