The details related to how the MRI data will be read and adjudicated will be outlined in a separate imaging charter. In the cases where the initial two readings are discrepant, a third reading is performed by an independent reader. This third score is not an adjudication but rather an additional score and value for analysis which will be based on the average of all 3 reader assessments. There will also be two sessions of readings. The first session will conduct readings of the Baseline and Week 12 MRI and will be used for summaries at Week 12. The second session will conduct readings of the Baseline, Week 12 and Week 52 MRIs and will be used for summaries at Week 52.

The following visit windows will be applied:

- All Baseline values should be collected prior to randomization as MRI is required to be randomized into the study.
- With the exception of Week 156, for post-Baseline visits, a time window of 2 weeks before or after the scheduled visit will be used for mapping MRI data to the given visit.
- For Week 156, a time window of 4 weeks before or after the scheduled visit will be used for MRI data to the given visit. The expected day for Week 156 will be calculated assuming that the SFE period start was on Week 52. I.e. Week 156 will be expected to be  $(156-52) \times 7$  days after Week 52. For patients where the first dose after the Week 50 is before the SFE informed consent the width of the lower boundary of the Week 156 window will be increased further

by the absolute number of days between the first dose after the Week 50 visit and the SFE informed consent date.

The SI joint SPARCC data collected after the discontinuation of double-blind study treatment will be treated as missing for any observed case analysis.

The change from Baseline in SI joint SPARCC score at Week 12 is a secondary efficacy endpoint.

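### Section 8.2.2.2 step 2 imputes terminal gaps from placebo even in subjects still on CZP, which shrinks the SI joint SPARCC effect at Week 12 (test 8)

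*SAP*

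**What the plan says.** SAP Section 8.2.2.2 makes reference-based multiple imputation the primary method for the continuous secondary variables. Its stated premise is that the method "assumes that the statistical behavior of the CZP and placebo-treated subjects after discontinuing study medication becomes that of the placebo-treated subjects". The same paragraph describes the draws as replacing outcomes of subjects who discontinued.

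The numbered steps divide the work by missing-data pattern instead:

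- Step 1 fills intermittent gaps by MCMC with treatment, region and MRI/CRP class in the model.
- Step 2 takes whatever is still missing for every subject with a monotone pattern. These values are "imputed using regression using the placebo-treated subjects arm only to impute missing data for both placebo and CZP treatments".

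The section applies the same procedure to SI joint SPARCC at Week 12, while noting that "SPARCC score will not be measured at any time points between Baseline and Week 12". Section 8.2.1.4 adds that, for post-Baseline visits other than Week 156, "a time window of 2 weeks before or after the scheduled visit will be used for mapping MRI data to the given visit", and that a visit with all MRI scores unavailable gets a blank total. In Section 8, SPARCC at Week 12 is test 8 in both the main and the Canadian sequence.

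**The concern.** The premise concerns treatment status; the instruction concerns the pattern of missing data. The two differ for a subject who is still on CZP and lacks the last value needed. If a later score exists, step 1 imputes the gap with treatment in the model. If none exists, step 2 imputes the same kind of gap as though the subject were on placebo. No reason is given for making the assumption depend on whether a later visit was recorded.

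For SPARCC the second route is the only one. With two time points a missing Week 12 score is always terminal, and it is imputed from placebo using Baseline, region and MRI/CRP class alone. An absent scan, a wholly unreadable scan or one outside the window does not mean that the subject stopped CZP. The imputed values carry no drug effect, so the difference tested at step 8 is diluted. A failure there stops ASQoL, nocturnal spinal pain and anterior uveitis (tests 9–11) from being tested.

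**Working it through.** **The plan's own figure.** The only design figure is in Section 2.4: "A total sample size of 300 (150 subjects per treatment group) provides 95% power", with "The expected response rates for ASDAS-MI at Week 52 are 40% and 20% for CZP and placebo, respectively". The two-sided level is 0.05 and allocation is 1:1. Pooled rate 0.30:

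z = (0.20 − 1.96·√(2·0.30·0.70/150)) / √((0.40·0.60 + 0.20·0.80)/150) = (0.20 − 0.1037)/0.0516 = 1.865, so power is 96.9% (95.9% with continuity correction).

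The stated 95% is reproduced. It belongs to the primary endpoint, which does not use this imputation.

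**SPARCC at Week 12.** Let Δ be the true adjusted difference and m the share of CZP subjects on treatment with no usable Week 12 score. Assume that the gaps are unrelated to outcome given the covariates, and that nobody has discontinued by Week 12. The completed CZP mean is then (1 − m)·μ_CZP + m·μ_PBO. Gaps in the placebo arm are imputed correctly by the placebo model. So:

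expected estimate = (1 − m)·Δ.

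With 150 CZP subjects, m = 2%, 5%, 10% and 15% means 3, 7.5, 15 and 22.5 subjects.

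**Simulation.** Assumptions not taken from the SAP: standardised effect 0.3 or 0.4, correlation with Baseline 0.5, m equal in both arms. Settings: 150 per arm, ANCOVA with Rubin's rules, 20 imputations, 1,500 replicates. The comparison model includes treatment.

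| Effect | m | Estimate ÷ truth, as written | Power, as written | Power, treatment in model |
|---|---|---|---|---|
| 0.3 | 2% | 0.974 | 83.8% | 84.9% |
| 0.3 | 5% | 0.956 | 81.2% | 83.5% |
| 0.3 | 10% | 0.902 | 72.7% | 81.8% |
| 0.3 | 15% | 0.855 | 66.3% | 77.7% |
| 0.4 | 2% | 0.981 | 97.3% | 97.5% |
| 0.4 | 5% | 0.949 | 96.6% | 97.3% |
| 0.4 | 10% | 0.909 | 95.3% | 96.1% |
| 0.4 | 15% | 0.849 | 91.2% | 96.3% |

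The ratios follow 1 − m. With treatment in the model the ratio lies between 0.99 and 1.01. With no true effect, the rule as written rejects in 2.5–4.6% of replicates.

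**Week 52 scores (tests 6, 7, 9, 10).** Earlier on-treatment visits are predictors, so much of the drug effect survives. With b the regression weight on the previous visit and a similar effect at both visits, the factor is 1 − m(1 − b). For an assumed b of 0.6–0.9:

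- m = 5%: 0.98 to 0.995, a loss of 0.5–2%.
- m = 15%: at worst 1 − 0.15·0.4 = 0.94, a loss of 6%.

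**Week 12 BASDAI and BASFI (tests 3, 4).** Section 8.3 lists further scores from Week 16 on. A missed Week 12 score followed by an on-treatment score is intermittent and goes to step 1, provided later visits enter that model. Section 8.2.2.2 does not say which visits do.

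**The case against.** The scope may be deliberate. Section 4.2.2 describes the reference-based procedure as imputing missing data in addition to data collected after discontinuation, and Section 8.2.2.2 counts post-discontinuation data as only one part of what is missing. Treating every terminal gap as placebo is a legitimate conservative choice. That stands as a possible intention, but it does not reconcile step 2 with the premise stated beside it, or with step 1, which does use treatment for on-treatment gaps. Section 8.1.3.3 treats a monotone pattern as the result of discontinuation; the converse does not follow and cannot hold for a variable with two time points.

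Section 8.2.1.4 also deals with partly unreadable scans by counting unavailable scores as zero or carrying numeric scores forward. That stands: only absent, wholly unreadable or out-of-window scans reach step 2.

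Section 8.2.3 plans missing-at-random imputation and observed-case analyses, which would reveal a gap. They do not replace the confirmatory test.

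A reader might infer that all the reference-based tests (3, 4 and 6–10) are materially biased, or that the error could produce a false claim. The working supports neither: the loss sits mainly in test 8 and its direction is conservative. Tests 1, 2 and 5 are composite responder analyses and do not use this method.

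**Conclusion.** The contradiction between the stated assumption and step 2 is real and concerns a confirmatory analysis. Its practical weight falls on SI joint SPARCC at Week 12, where the estimate is about (1 − m) times the truth.

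The size is unknown. The SAP gives no missing-data rate and no SPARCC effect or SD, so the 2–15% range for m is an assumption. At a few per cent the loss is small: at m = 5%, power falls by 2.3 points for an effect of 0.3 and 0.7 points for 0.4, close to the simulation error of about 1 point at 80% power (√(0.8·0.2/1500) = 0.0103). At 10–15% with an effect of 0.3 it falls by 9 to 11 points. Type I error is not inflated. The cost is power at test 8 and, through the sequence, the chance to test 9–11.

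**What to change.** In Section 8.2.2.2 step 2, limit the placebo-arm regression to values missing after discontinuation of double-blind treatment. Impute values missing while the subject is still on double-blind treatment with the regression of Section 8.2.3.1 step 2, which includes treatment arm. Name SPARCC explicitly, because Section 8.2.3.1 lists only BASDAI, BASFI, ASQoL and nocturnal spinal pain; for SPARCC the earlier measurement is Baseline. State which visits enter step 1. Keep the all-placebo version as a sensitivity analysis.

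Before code release this costs a change of wording and an on/off-treatment flag in the imputation program. The downside is a slightly less conservative test.

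Timing matters. Section 4.3 makes treatment codes available to the reporting team at the Week 52 lock, and Sections 2.2.1.3 and 8.1.1 refer to double-blind outputs already produced. If the codes are out, replacing the confirmatory rule would be an unblinded change in favour of CZP. In that case keep the pre-specified test as run, report by arm and variable how many on-treatment values were imputed from placebo, and present the corrected version as supplementary.
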